### 8.2 *Administration, Dosage and Duration of Treatment*

Study drug will be administered orally (via syringe) **with food** according to the following treatment schedule:

- Initial starting dose (Day 1 p.m. dose to Day 3 a.m. dose):  
5 mg/kg of body weight CardiolRx™ b.i.d.
- Day 3 p.m. dose to Day 10 a.m. dose:  
7.5 mg/kg of body weight CardiolRx™ b.i.d.
- Day 10 p.m. dose to end of study (a.m. dose at Week 26):  
10.0 mg/kg of body weight CardiolRx™ b.i.d.
- The morning and evening doses should be taken minimally 6 hours and maximally 18 hours between each intake.

If the next higher dose is not tolerated, the patient should return to the last tolerated dose. The highest tolerated dose should be administered until the end of the study (26 weeks post start of study medication).

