8.4 Study drug exposure

The study drug exposure will be presented using the variables listed below:

Variable	Formula
Total dose planned per protocol for patients enrolled under protocol amendment 1 (mL) [PLANNED_DOSE]	
Weight (in kg) * 3.68 mL/kg for patients who agreed to do the extension
 
Where 3.68 mL/kg=
 $(2 \text{ days} * 2.5 \text{ mg/kg bid} * 2 + 4 \text{ days} * 5 \text{ mg/kg bid} * 2 + 7 \text{ days} * 7.5 \text{ mg/kg bid} * 2 + 167 \text{ days} * 10 \text{ mg/kg bid} * 2) / 950 \text{ mg/mL}$ 
Or
 
Weight (in kg) * 1.07 mL/kg for patients who stopped the study at 8 weeks
 
Where 1.07 mL/kg=
 $(2 \text{ days} * 2.5 \text{ mg/kg bid} * 2 + 4 \text{ days} * 5 \text{ mg/kg bid} * 2 + 7 \text{ days} * 7.5 \text{ mg/kg bid} * 2 + 43 \text{ days} * 10 \text{ mg/kg bid} * 2) / 950 \text{ mg/mL}$
Total dose planned for patients enrolled under protocol amendment 1 (mL) based on visits actually performed	$\text{weight (in kg)} * \sum_{i=1}^{10} \text{planned dose (mg/kg bid) documented at visit i} * 2 * (\text{visit date (i + 1)} - \text{visit date (i)})$
Total dose planned for patients enrolled under protocol amendment 2 (mL) [PLANNED_DOSE]	
Weight (in kg) * 3.73 mL/kg for patients who agreed to do the extension
 
Where 3.73 mL/kg=
 $(2 \text{ days} * 5 \text{ mg/kg bid} * 2 + 7 \text{ days} * 7.5 \text{ mg/kg bid} * 2 + 171 \text{ days} * 10 \text{ mg/kg bid} * 2) / 950 \text{ mg/mL}$ 
Or

Variable	Formula
	
Weight (in kg) * 1.11 mL/kg for patients who stopped the study at 8 weeks
 
Where 1.11 mL/kg=
 $ \begin{aligned} & (2 \text{ days} * 5 \text{ mg/kg bid} * 2 \\ & + 7 \text{ days} * 7.5 \text{ mg/kg bid} * 2 \\ & + 47 \text{ days} * 10 \text{ mg/kg bid} * 2) / 950 \text{ mg/mL} \end{aligned} $
Total dose planned for patients enrolled under protocol amendment 2 (mL) based on visits actually performed	$ \text{weight (in kg)} * \sum_{i=1}^8 \text{planned dose (mg/kg bid) documented at visit } i * 2 * (\text{visit date } (i+1) - \text{visit date } (i)) $

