Total dose taken (mL) [DOSE_TAKEN]	$ \sum_{j=1}^{\# \text{ bottles returned}} \frac{78 \text{ g} - \text{bottle weight in g (j)}}{0.95 \text{ [g/mL]}} $ 
If there is no bottle weight and the reason is:
 
 • 'Bottle broken', imputed weight to 48g • 'Unused bottle', imputed weight to 78g 
Note: 'Already weighted' should not be considered.
 $ + \sum_{k=1}^{\# \text{ bottles unreturned}} \frac{78 \text{ g} - \text{imputed bottle weight (k)}}{0.95 \text{ [g/mL]}} $ 
Imputed weight if the status of the unreturned IMP bottle is:
 
 • 'Unused', imputed weight to 78g • 'Empty', imputed weight to 48g • Other reasons, i.e., 'Used per instructions', 'Not used per instructions', 'Unknown' must be reviewed during DRM.
Compliance global (%)	[DOSE_TAKEN] / [PLANNED_DOSE]
# days during which patients were taking the IMP	Last date under medication – first date under medication – the sum of all temporary interruption (end date of interruption – start date of interruption +1)
# patients who did not complete 8 weeks on IMP	# of patients with Premature withdrawal of study treatment form completed before the Week 8 visit date
# patients who stopped the IMP prematurely (i.e. prior to or at week 8)	# of patients with Premature withdrawal of study treatment form with a premature withdrawal date \leq Week 8 visit date

Variable	Formula
# patients with highest tolerated IMP dose up to Week 8	
# of patients for whom the maximum dose taken up to the week 8 visit date was:
 
 • 10mg/kg of body weight b.i.d. • 7.5mg/kg of body weight b.i.d. • 5.0mg/kg of body weight b.i.d.
# patients with highest tolerated IMP dose over the complete follow-up period	
# of patients for whom the maximum dose taken up to the last IMP intake was:
 
 • 10mg/kg of body weight b.i.d. • 7.5mg/kg of body weight b.i.d. • 5.0mg/kg of body weight b.i.d.

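### Global compliance in SAP 8.4 scores permitted dose reductions and stops as non-compliance, and its planned volume is 9.5 times too small at the protocol's stated concentration

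*SAP*

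**What the plan says.** SAP 8.4 has one compliance measure, "DOSE_TAKEN] / [PLANNED_DOSE". The numerator is a volume of solution, obtained from bottle weights and a density of 0.95 g/mL.

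The PLANNED_DOSE tag is attached only to fixed schedules:

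- Amendment 1: "Weight (in kg) * 3.68 mL/kg for patients who agreed to do the extension", or "Weight (in kg) * 1.07 mL/kg for patients who stopped the study at 8 weeks".
- Amendment 2: "Weight (in kg) * 3.73 mL/kg for patients who agreed to do the extension", or "Weight (in kg) * 1.11 mL/kg for patients who stopped the study at 8 weeks".

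Each constant is the mg/kg total of the full titration schedule divided by 950 mg/mL. Protocol 6.4 and 8.1 give the product concentration as 100 mg/mL.

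A separate row, "Total dose planned for patients enrolled under protocol amendment 2 (mL) based on visits actually performed", sums the dose documented at each visit over the actual visit intervals. Amendment 1 has a matching row. Neither carries the PLANNED_DOSE tag, so neither enters the compliance ratio.

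On dosing, Protocol 8.2 sends a patient who cannot tolerate a step back to the last tolerated dose and adds: "The highest tolerated dose should be administered until the end of the study". Protocol 6.5.1 and 9.2.3 list cases in which study drug must be stopped. Section 6.5.2 allows interruptions of up to 7 days. Under Visit 2 in Section 9.1, a patient who does not tolerate the starting dose stops the drug but stays in follow-up to Visit 5.

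**The concern.** A compliance figure should say how much of the prescribed drug was taken. This denominator is not what was prescribed for anyone who was reduced, interrupted or taken off drug under the protocol. For those patients the ratio mixes tolerability and discontinuation with adherence, in a pilot whose stated purpose includes assessing tolerance. SAP 8.4 itself expects such patients, since it tabulates 7.5 and 5.0 mg/kg b.i.d. as possible highest tolerated doses.

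There is also a unit problem. The divisor 950 mg/mL is numerically the 0.95 g/mL density used for the bottle weights. It is a mass of solution per mL, not a mass of cannabidiol per mL. If the numerator is mL of a 100 mg/mL solution, the two halves of the ratio are on different scales.

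At stake is the accuracy and meaning of one reported exposure result (SAP Table 15).

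**Working it through.** **Inputs.** Schedules, constants and bottle weights are from SAP 8.4. The concentration of 100 mg/mL is from Protocol 6.4 and 8.1, and the 30 mL bottle from Protocol 8.4.1. I assume constant body weight, and that a reduced patient is held at the lower dose from the first step not tolerated.

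**Step 1: reproduce the SAP constants.** Planned mL/kg = sum of (days × mg/kg × 2) / 950.

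| Schedule | mg/kg total | /950 | SAP states | /100 |
|---|---|---|---|---|
| Amendment 1, 26 weeks | 10 + 40 + 105 + 3340 = 3495 | 3.679 | 3.68 | 34.95 |
| Amendment 1, 8 weeks | 10 + 40 + 105 + 860 = 1015 | 1.068 | 1.07 | 10.15 |
| Amendment 2, 26 weeks | 20 + 105 + 3420 = 3545 | 3.732 | 3.73 | 35.45 |
| Amendment 2, 8 weeks | 20 + 105 + 940 = 1065 | 1.121 | 1.11 | 10.65 |

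Three constants match. The fourth rounds to 1.12, a 1% slip.

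**Step 2: the denominator effect on consistent units.** Every prescribed dose is taken, and the ratio is mg taken / mg planned.

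- Amendment 2, 26 weeks, held at 7.5 mg/kg b.i.d.: (20 + 178 × 15) / 3545 = 2690/3545 = 75.9%.
- Amendment 2, 26 weeks, held at 5 mg/kg b.i.d.: (180 × 10) / 3545 = 1800/3545 = 50.8%.
- Amendment 2, extension patient who stops at Week 12 (84 days): (20 + 105 + 75 × 20) / 3545 = 1625/3545 = 45.8%.
- Amendment 2, 8 weeks: 830/1065 = 77.9% at 7.5 and 560/1065 = 52.6% at 5 mg/kg b.i.d.
- Amendment 2, starting dose not tolerated, stopped after 2 days, 56-day denominator: 20/1065 = 1.9%.
- Amendment 1: 76.1% and 51.2% at 26 weeks; 78.8% and 54.2% at 8 weeks.

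If the higher dose is tried first (12 days at 10 before 7.5, or 7 days at 7.5 before 5 mg/kg b.i.d.), the Amendment 2 26-week ratios become 2750/3545 = 77.6% and 1835/3545 = 51.8%.

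**Step 3: the formula as printed.** The numerator is volume of solution: an empty bottle counts as (78 − 48) / 0.95 = 31.6 mL, close to the 30 mL bottle. At 100 mg/mL, a fully dosed Amendment 2 extension patient takes 35.45 mL/kg against 3.73 mL/kg planned.

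- Never reduced: 35.45 / 3.73 = 950%.
- Held at 7.5 mg/kg b.i.d.: 26.90 / 3.73 = 721%.
- Held at 5 mg/kg b.i.d.: 18.00 / 3.73 = 483%.

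For an illustrative 70 kg patient the plan is 3.73 × 70 = 261 mL, against 35.45 × 70 = 2481.5 mL. The factor is 950/100 = 9.5.

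**Step 4: are the two errors separate?** Yes. 483/950 = 51% and 721/950 = 76%, so the relative distortion from the denominator survives any change of divisor.

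**Step 5: the visit-based row.** Its terms are kg × mg/kg × doses per day × days, which give mg. The row is labelled mL and no division by a concentration is printed.

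**The case against.** The best defence is that dose taken against the full protocol plan is a legitimate, disclosed summary. The same section reports the visit-based planned dose, days on drug net of interruptions, stops by Week 8 and highest tolerated dose, so a reader has the context. Patients who stop the study at 8 weeks do get a shorter denominator. Compliance feeds nothing else: SAP 5 defines only sets based on starting drug, there is no per-protocol set, and no inferential analysis is planned.

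Much of this stands. It limits the consequence and rules out saying that every early stop is mishandled. It does not rescue the measure. The neighbouring rows describe the group and do not turn the ratio into adherence. The 8-week constant covers one stopping time only, and stopping drug is not the same as stopping the study (Protocol 6.5.1). The divisor is an inconsistency whatever the ratio is called.

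Two stronger readings are tempting. A reader might infer that the SAP table would show adherent patients at 50–76%. It would not: those values need consistent units and apply to 26-week patients on a reduced dose, while early stoppers can fall well outside that range. A reader might also infer that a low figure would be used to explain away a weak effect. Nothing in the documents links compliance to the interpretation of efficacy.

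**Conclusion.** The point holds for the exposure table. The denominator counts permitted reductions, interruptions and stops at other times as non-compliance. On consistent units this costs an adherent Amendment 2 26-week patient about 24 percentage points at 7.5 mg/kg b.i.d. and 49 at 5 mg/kg b.i.d. Separately, the printed divisor inflates every score 9.5-fold if the solution is 100 mg/mL as the protocol states.

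The documents give no expected rate of dose reduction, so the effect on the group mean is unknown. As a scale, in 25 otherwise fully adherent 26-week patients, each patient held at 5 mg/kg b.i.d. lowers the mean by 49.2/25 = 2.0 points, and each held at 7.5 mg/kg b.i.d. by 24.1/25 = 1.0 point.

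No efficacy estimate or analysis set is affected. The results rest on constant weight, all solution at 100 mg/mL and the reduction patterns stated above. Values near 950% would probably be noticed, but correcting only the divisor would leave the denominator problem in place.

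**What to change.** 1. Reconcile the 950 mg/mL divisor with the protocol's 100 mg/mL and recompute the four constants. At 100 mg/mL they are 34.95 and 10.15 mL/kg (Amendment 1) and 35.45 and 10.65 mL/kg (Amendment 2), for 26 and 8 weeks respectively.
2. Divide the visit-based planned dose by the same concentration, so that it is in mL as labelled.
3. Define compliance as DOSE_TAKEN divided by the visit-based prescribed dose up to the last dose date, net of recorded interruptions. State how a dose change between visits is counted.
4. If the full-schedule ratio is kept, report it with the corrected divisor as relative dose intensity.

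The cost is SAP wording and some reprogramming, with no new data collection evident. Visit dates, documented doses, last date on drug and interruption dates already appear in SAP 8.4. The truncation and interruption rules are new derivations and should be written down before the exposure table is produced. No dosing rule changes.

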### ***10.3 Description of Patient Groups for Analyses***

#### **10.3.1 Population for Efficacy and Safety Analyses**

All patients who were enrolled and took at least one dose of study medication will be included in the safety analyses.

Patients who do not tolerate the initial dose of 5 mg/kg of body weight b.i.d. will stay in the study for safety evaluations but will be replaced for the assessment of efficacy.

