4 STUDY POPULATION

We present in this section, the inclusion/exclusion criteria as detailed in protocol amendment 2 and compare the changes to protocol amendment 1 to take into consideration the 6 patients enrolled under protocol amendment 1.

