4.3 Study treatment assignment

Per protocol amendment 2, eligible patients would receive open label IMP (i.e. CardiolRxTM).

The dosing regimen was as follows:

- Day 1 p.m. to Day 3 a.m. dose: 5 mg/kg of body weight b.i.d. First dose to be taken in the evening of the screening visit (i.e. day 1)
- Day 3 p.m. dose to Day 10 a.m. dose: 7.5 mg/kg of body weight b.i.d. Dose titration if previous dose tolerated
- Day 10 p.m. dose to end of treatment period (a.m. dose at either week 8 or am dose week 26 if patient continued in the EP phase of the trial): 10 mg/kg of body weight b.i.d. Dose titration if previous dose tolerated

The morning and evening doses should be taken minimally 6 and maximally 18 hours apart. If the next higher dose after each study drug increase was not tolerated, the site could reduce the dose to the previous tolerated dose.

Difference between protocol amendments 1 and 2 and the (potential) impact on the statistical Analysis

Protocol amendment 1: Administration of IMP was planned as follows²:

- Day 1 p.m. dose to Day 3 a.m. dose: 2.5 mg/kg of body weight b.i.d.
- Day 3 p.m. dose to Day 7 a.m. dose: 5.0 mg/kg of body weight b.i.d.
- Day 7 p.m. dose to Day 14 a.m. dose: 7.5 mg/kg of body weight b.i.d.
- Day 14 p.m. dose to end of treatment period (a.m. dose at week 26, i.e Day 181): 10.0 mg/kg of body weight b.i.d

Impact on the statistical Analysis Plan:

The difference in the overall dose is an increase of 5% (i.e. starting dose was 2.5 mg/kg of body weight b.i.d for protocol amendment 1 and 5 mg/kg of body weight b.i.d for amendment 2). This may potentially impact on the primary endpoint at 8 weeks and on the total dose taken over the study duration.

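### SAP 8.4 derives the highest tolerated dose as the maximum dose taken, which conflicts with protocol 8.2 and, read literally, classifies stepped-down patients at a dose they did not tolerate

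*SAP*

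**What the plan says.** The exposure table in SAP 8.4 has two rows on this variable. The first is labelled as the number of "patients with highest tolerated IMP dose up to Week 8" and is computed as the number of "patients for whom the maximum dose taken up to the week 8 visit date was" one of three levels: 10, 7.5 or 5.0 mg/kg b.i.d. The second covers the whole follow-up with the same three levels and counts "patients for whom the maximum dose taken up to the last IMP intake was" each of them. These rows feed SAP Table 15.

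Protocol 8.2 gives the term another meaning: "If the next higher dose is not tolerated, the patient should return to the last tolerated dose", and then "The highest tolerated dose should be administered until the end of the study". Protocol 9.1 spells out the step-downs, from 7.5 to 5 at Visit 3 and from 10 to 7.5 at Visit 4. Protocol 6.5.1 and Visit 2 in 9.1 stop study drug in a patient who cannot tolerate the 5 mg/kg start. Protocol 10.3.1 keeps that patient in: "Patients who do not tolerate the initial dose of 5 mg/kg of body weight b.i.d. will stay in the study for safety evaluations".

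SAP section 4 refers to "the 6 patients enrolled under protocol amendment 1". SAP 4.3 gives their first step as "Day 1 p.m. dose to Day 3 a.m. dose: 2.5 mg/kg of body weight b.i.d".

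The SAP's list of tables also names a Table 7-1 on complex cases of the highest tolerated dose. By its number it belongs to section 7, the staged analysis. Its content is not in the text available, and the dose list in section 7 breaks off after 5.0 mg/kg.

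**The concern.** Under a forced titration with step-down, the maximum dose taken and the highest dose tolerated differ for exactly the patients who had a tolerability problem. A row labelled with the second quantity but computed from the first can err in one direction only: it makes the drug look better tolerated.

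The protocol's rationale (synopsis and section 3.5) names tolerance and safety as a purpose of the pilot. Someone reading Table 15 would take the share of patients at 10 mg/kg as the share who could stay on it. A programmer working from 8.4 alone would code the maximum.

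**Working it through.** The plan states no count or percentage for this variable, so there is no figure to reproduce. The check applies the literal 8.4 rule to dose paths that the documents allow and compares the result with the meaning in protocol 8.2.

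Inputs: the rule and its three categories (SAP 8.4); the step-down rule (protocol 8.2 and 9.1); stopping after intolerance of the starting dose (protocol 6.5.1); the Amendment 1 starting dose of 2.5 mg/kg (SAP 4.3); 6 patients under Amendment 1 (SAP section 4); about 25 patients planned (protocol 5.1). One assumption: Amendment 1 patients could also step back after an increase that was not tolerated.

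| Path (mg/kg b.i.d.) | Literal 8.4 | Protocol 8.2 meaning |
|---|---|---|
| Amendment 2: 5, 7.5, 10, stays | 10 | 10 |
| Amendment 2: 5, 7.5, 10, back to 7.5 | 10 | 7.5 |
| Amendment 2: 5, 7.5, back to 5 | 7.5 | 5 |
| Amendment 2: 5 not tolerated, stopped | 5 | none |
| Amendment 1: 2.5, 5, back to 2.5 | 5 | 2.5 |
| Amendment 1: never above 2.5 (tolerated) | no category | 2.5 |

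The literal rule agrees with the protocol on one of the six paths, overstates on four and has no category on one. These are types of path, not frequencies of patients.

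The last two rows differ in kind. A patient who steps back from 5 to 2.5 does get a category under 8.4, but it is the 5.0 row. Only a patient who never exceeded 2.5 is left without one.

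Size, with N = 25:
- One affected patient: 1/25 = 4 percentage points.
- Assumed range of 1 to 3 affected patients: 1/25 to 3/25 = 4 to 12 points.
- Ceiling for the missing 2.5 row: 6/25 = 24%. Nothing shows that any of the six stayed at 2.5, a step planned to last only from the evening of Day 1 to the morning of Day 3.

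**The case against.** The strongest reply is Table 7-1. The SAP has a table devoted to complex cases of this same variable, and patients who tried a dose and were reduced, or who stayed at 2.5 mg/kg, are its natural candidates. Content that cannot be seen cannot be counted as missing from the plan. A reader might infer that the trial will report failed doses as tolerated, or that 2.5 mg/kg has no category anywhere in the SAP. Neither is supported: both gaps are shown for 8.4 only. Nor can one infer that the staged and final results will disagree, because the reach of Table 7-1 is unknown.

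What the reply does not remove is the conflict inside the visible text. Section 8.4 states its formula without qualification and without pointing to Table 7-1, although the SAP cross-refers elsewhere: section 7 points to 8.5.1 and 8.5.2, and 8.4 itself sends unclear bottle statuses to the data review meeting. The section 7 item runs only to Week 8, and no visible text carries Table 7-1 over to the whole-follow-up row. If Table 7-1 does classify stepped-down patients at the lower dose, it contradicts the Week 8 row of 8.4. If it does not, 8.4 contradicts the protocol. Reconciliation is needed either way.

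It is also fair to say that this is a descriptive row, that no inference is planned, and that tolerability shows up as well in the adverse event tables, the premature-stop counts and the withdrawal listing. That limits the consequence but does not make the row correct.

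**Conclusion.** The point holds for SAP 8.4 as written. At both horizons the label and the derivation describe different quantities. The derivation conflicts with protocol 8.2, and its error always runs towards better tolerability. The missing 2.5 mg/kg row is a narrower gap: it concerns at most 6 patients, and only any who never exceeded that dose.

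The number of patients affected is not in the documents. The figure of about 4 points each assumes N = 25 and that 8.4 is applied without correction from Table 7-1.

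Two further inferences should be resisted. One is that the table would show every patient at 10 mg/kg. That would require all of them to have reached that dose, whereas the protocol foresees patients stopping at 5 or returning to it from 7.5. The other is that this row would set the dose of the next trial. Protocol 3.5 says only that the results inform the feasibility of designing one. No efficacy endpoint depends on the variable.

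**What to change.** In SAP 8.4:

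1. Rename the two existing rows as maximum dose taken, up to Week 8 and up to last intake.
2. Add rows for highest tolerated dose at both horizons, derived consistently with protocol 8.2. Refer explicitly to Table 7-1 and reconcile the two, so that one rule applies throughout.
3. Add a 2.5 mg/kg category and a category for patients with no tolerated dose.
4. State the data source. The documents show the dose recorded by visit but not that the reason for a reduction is captured. If it is not, use the dose continued after the reduction and settle unclear cases at the data review meeting.

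The cost is SAP wording and minor programming for Table 15. If reasons for reduction were not collected, some case review is added. No dosing rule and no efficacy analysis changes.

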8.5 Efficacy analysis

Given the small sample size and the design of the study, no inferential statistical analyses are planned. All data collected during a scheduled visit (except the NRS score which was collected daily) will be included in the descriptive statistics.

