## **6.7 Management of Pericarditis Recurrence During the Extension Period**

Pericarditis recurrence during the extension period is defined as the recurrence of typical pericarditis pain associated with supportive objective evidence of pericarditis in the opinion of the investigator. At any timepoint during the EP, patients who experience suspected recurrence of their pericarditis will have been instructed to inform their site Investigator as soon as possible. Patients who experience a suspected recurrence of pericarditis symptoms will be requested to report to the study site/clinic for a scheduled or unscheduled visit, during which clinical assessments will be performed to gather all the necessary diagnostic data to confirm or rule out the presence of pericarditis recurrence. The Investigator will evaluate all assessments performed for a diagnostic workup, whether at the study site or at locations outside.

Following communication with the study medical monitor, patients who report at least 1 day with pericarditis pain measurement  $\geq 4$  on the 11-point NRS **AND** have a CRP value  $\geq 1$  mg/dL (either on the same day or separated by no more than 7 days) during the EP of the trial will receive rescue therapy at the discretion of the investigator, i.e., if not already taking; analgesics first, then NSAIDs, and then colchicine. Immunosuppressive therapy such as corticosteroids or rilonacept may be added for pericarditis recurrence at the discretion of the investigator.

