## 11 STATISTICAL METHODS

### 11.1 Sample Size Estimation

No formal sample size was calculated for this Pilot study. Approximately 25 patients will be included in this study. Patients who do not tolerate the initial dose of 5 mg/kg of body weight b.i.d. will stay in the study for safety evaluations but will be replaced for the assessment of efficacy.

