7 STAGED STATISTICAL ANALYSIS (SSA)

As mentioned in section 1, the analyses for this trial will be done in a staged manner – i.e. the first analysis will be performed for data collected up to the week 8 visit and the second analysis will be done when the last patient last visit is performed and the database is declared ready for complete database lock. The following data will be presented in the SSA:

- Baseline data for all patients enrolled:
 - Patient demographics: age, gender, race, ethnicity
 - Past medical history: N (%) of patients by previous episodes of pericarditis category (i.e., 2, 3, 4, or >4);
 - N (%) of patients for whom medications at baseline were prescribed for pain and pericarditis: analgesics, opiates, NSAIDs, colchicine and corticosteroids. The medications concerned will be identified as those with following

Anatomical Therapeutic Chemical (ATC) classification: H02 (Corticosteroids for systemic use), M01 (anti-inflammatory and antirheumatic products), M04 (antigout preparations), N02A (Opioids), N02B (other analgesics and antipyretics)

- N (%) of patients prescribed medications for pain and pericarditis i.e. medications which were started up to and including the Week 8 visit date and for which the stop date was either empty or > enrolment date at the time of enrolment
- CRP value at baseline will be summarized as a continuous variable
- NRS scores at baseline will be summarized as a continuous variable
- Primary efficacy endpoint, i.e. the change in patient-reported pericarditis pain using an 11-point NRS from baseline to 8 weeks – see section 8.5.1.
- Additional efficacy endpoints (see section 8.5.2):
 - Patients with normalized CRP levels (i.e. with a CRP \leq 0.5 mg/dL) at 8 weeks (for patients with CRP \geq 1.0 mg/dL at baseline) will be summarized as a categorical variable.
 - Time to CRP normalization (in days – see section 8.5.2) up to the Week 8 visit date for patients with CRP \geq 1.0 mg/dL at baseline will be summarized as a continuous variable. If CRP had not normalized at the timepoint assessed in the analysis (e.g. week 8), the patients concerned was not included in the analysis - Time to CRP normalization
 - CRP change from baseline at 8 weeks will be summarized as a continuous variable.
- Study drug exposure:
 - N (%) of patients with highest tolerated dose of (up to Week 8 visit date):
 - 10mg/kg of body weight b.i.d.
 - 7.5mg/kg of body weight b.i.d.
 - 5.0mg/kg of body weight b.i.d.

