8.5.1 Primary efficacy analysis

The 11-point NRS value for a specific week will be determined by the worst NRS score collected on the daily NRS questionnaire for the seven days prior (day – 7 to day -1) to the week 8 visit (or planned visit date if week 8 visit not performed). If the daily NRS questionnaire is not completed for 7 consecutive days prior to the week 8 visit, the worst NRS score between the eCRF (Item: What is the highest NRS score over the past 7 days according to the patient?) and the NRS questionnaire completed by the patient will be used. The change in patient-reported pericarditis pain using an 11-point NRS from baseline to 8 weeks will be presented as a continuous variable.

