8.5.2 Additional efficacy analysis

- The change in patient-reported pericarditis pain using an 11-point NRS from baseline to 26 weeks will be summarized as a continuous variable.
- The change in patient-reported pericarditis pain using an 11-point NRS from baseline to other intermediate weeks (i.e. visits 3,4,5,6,7) will be summarized as a continuous variable.
- Patients with normalized CRP levels (i.e with a CRP \leq 0.5 mg/dL) at 8 weeks (for patients with CRP \geq 1.0 mg/dL at baseline) will be summarized as a categorical variable
- Patients with normalized CRP levels (i.e with a CRP \leq 0.5 mg/dL) at 26 weeks (for patients with CRP \geq 1.0 mg/dL at baseline) will be summarized as a categorical variable
- Patients with pericarditis recurrence during the extension period (EP), i.e with an adverse event occurring between week 8 and week 26 and coded with the following LLT code 10087207 (Recurrent pericarditis) will be summarized as a categorical variable

- Time to CRP normalization (in days) (i.e time between IMP start date up to the first blood draw date when $CRP \leq 0.5 \text{ mg/dL}$) for patients with $CRP \geq 1.0 \text{ mg/dL}$ at baseline will be summarized as a continuous variable. If CRP had not normalized at the timepoint assessed (i.e 8 week visit date (for SSA) or 26 weeks visit date for the final analysis), the patients concerned will not be included in the analysis for this outcome.
- CRP change from baseline at 26 weeks (%) will be summarized as a continuous variable.

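### Week 26 pain change has no rule for scores obtained after rescue therapy, so a patient who fails and is then rescued can count as improved

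*SAP*

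**What the plan says.** The trial has one arm, and its primary objective (Protocol 4.1.1) is to evaluate the effect of treatment. The analysis is descriptive: "Given the small sample size and the design of the study, no inferential statistical analyses are planned" (SAP 8.5). The same section adds: "All data collected during a scheduled visit (except the NRS score which was collected daily) will be included in the descriptive statistics".

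The Week 8 score is the "worst NRS score collected on the daily NRS questionnaire for the seven days prior (day – 7 to day -1) to the week 8 visit" (SAP 8.5.1), and "The change in patient-reported pericarditis pain using an 11-point NRS from baseline to 8 weeks will be presented as a continuous variable". For Week 26, SAP 8.5.2 states only that "The change in patient-reported pericarditis pain using an 11-point NRS from baseline to 26 weeks will be summarized as a continuous variable". Neither section mentions concomitant therapy. The Full Analysis Set (SAP 5.1) is everyone enrolled who started the drug.

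Protocol 5.2 requires stable background doses at entry. After Day 1, changes are recorded at each visit (Protocol 9.1 and 9.2.8). Protocol 6.6 prohibits named immunosuppressants, cannabinoids and strong enzyme inducers, and new QT-prolonging drugs. It does not in general bar starting or increasing analgesics, NSAIDs or corticosteroids before Week 8.

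In the extension period, Protocol 6.7 provides rescue (analgesics, NSAIDs, colchicine) for patients with a pain score of at least 4 together with CRP of at least 1 mg/dL. It adds: "Immunosuppressive therapy such as corticosteroids or rilonacept may be added for pericarditis recurrence at the discretion of the investigator".

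Two parts of the SAP touch on this. Section 8.5.3 lists an exploratory correlation between pericarditis medications and the pain score. Section 7 tabulates medications at baseline, and also "medications which were started up to and including the Week 8 visit date and for which the stop date was either empty" or later than enrolment.

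**The concern.** Under Protocol 6.7, rescue follows a measured failure. If it works, the patient's pain falls, and because the score covers only the last seven days, a flare treated earlier leaves no trace in it. The patient then contributes an improvement to the Week 26 mean. With no control arm, a reader has nothing in that mean to separate pain relief on study drug from pain relief on added drugs.

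This matters for how the result is used. Protocol 3.5 says that the pilot will inform the feasibility of a randomised withdrawal trial. SAP 8.5.3 also plans a numerical comparison with earlier rilonacept trials, under a separate SAP. Unless that document deals with rescue, scores lowered by rescue rilonacept could be set beside rilonacept's own results.

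**Working it through.** **No figure to reproduce.** The protocol states: "No formal sample size was calculated for this Pilot study. Approximately 25 patients will be included in this study". There is no power calculation, assumed effect or SD. The check is therefore of the text, followed by an illustration on stated assumptions.

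**Which scores can be affected**

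| | Week 8 | Week 26 |
|---|---|---|
| Rescue pathway described | No; Protocol 6.7 applies to the extension period, which starts after Visit 5 | Yes |
| Rescue rilonacept | Cannot apply | Can apply under 6.7 |
| Added analgesics, NSAIDs, corticosteroids | Recorded, not barred | Allowed as rescue |
| Planned background change | None; stable doses at entry | NSAIDs, corticosteroids and colchicine weaned (6.6) |
| Rule for scores after added therapy | None in SAP 8.5.1 | None in SAP 8.5.2 |

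**Whether another output fills the gap**

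- *Correlation (SAP 8.5.3).* No method is given, and no table for it appears in SAP Section 10, which SAP Section 8 calls the complete set. It does not separate added drugs from background drugs being weaned.
- *Section 7 medication rows.* The second row appears to contain the first, so comparing them by class might count new starts. It would not show dose increases or which patients were affected. It stops at Week 8.
- *Listing 4* shows medications but is not linked to pain scores.

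**Illustration for Week 26.** Let f be the fraction rescued and r the points by which rescue lowers a rescued patient's score. Shift in mean change = f × r. Both inputs are assumptions. Protocol 3.1 expects further episodes in 20% to 40% of patients with two or more recurrences, with no time window given, and the stopping guideline (Protocol 11.5) acts only above 50%. I therefore take f from 0.2 to 0.5, and r from 2 to 6.

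| f | r = 2 | r = 4 | r = 6 |
|---|---|---|---|
| 0.2 | 0.4 | 0.8 | 1.2 |
| 0.4 | 0.8 | 1.6 | 2.4 |
| 0.5 | 1.0 | 2.0 | 3.0 |

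If the recurrence probability is 20%, the chance of at least one recurrence among 25 patients is 1 − 0.8^25 = 0.996; at 40% it exceeds 0.999. Recurrence is not the same as rescue, but the situation is likely to arise.

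**Illustration for Week 8.** Each patient with added therapy moves the mean by r/25: 2/25 = 0.08 to 6/25 = 0.24 points.

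**What a set-to-baseline row would show.** If rescued patients fall by a points and the others by b, the all-data mean change is −[fa + (1 − f)b], the set-to-baseline mean is −(1 − f)b, and the gap is fa. With assumed a = 5 and b = 2.5:

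| f | All data | Set to baseline | Gap |
|---|---|---|---|
| 0.1 | −2.75 | −2.25 | 0.5 |
| 0.2 | −3.00 | −2.00 | 1.0 |
| 0.3 | −3.25 | −1.75 | 1.5 |

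**The case against.** The strongest defence is that including every observed score, whatever was added, is a coherent treatment-policy summary for a descriptive pilot. That stands, and it is why the all-data summary should stay.

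The direction of the net bias is also open. Weaning in the extension period tends to raise pain, which works against the drug. And if patients who need added drugs improve less than the others (a below b), pooling makes the mean look worse than that of the unrescued patients, not better. Even with a = 5 and b = 2.5, the all-data mean exceeds the unrescued mean by only f(a − b) = 0.25 to 0.75 points; the rest of the 0.5 to 1.5 gap comes from assigning zero change. So the set-to-baseline row is a convention, not an estimate of what would have happened without rescue.

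A reader might infer four stronger things, none of which the documents support:

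- *That the inclusion sentence in SAP 8.5 sweeps post-rescue pain scores in.* Its parenthesis exempts the pain score; the gap is the silence of 8.5.1 and 8.5.2.
- *That rescue rilonacept contaminates the Week 8 primary endpoint.* Rescue is described only after Week 8.
- *That recurrence is hidden.* It is a separate endpoint with its own Table 21. It is masked only within the pain mean.
- *That nothing on medication is planned.* The correlation and the Section 7 rows are planned, though they do not answer the question. Part of Section 7 is not in the text available for review, so nothing here rests on its silence.

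**Conclusion.** The point holds for Week 26, and to a lesser degree for Week 8. The plan does not say how pain scores after added or rescue therapy are handled. In a single-arm study a successfully rescued patient can therefore count as improved, and no specified output lets a reader see by how much.

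The size cannot be taken from the documents. The 0.4 to 3.0 points at Week 26 rests on 20% to 50% rescued, 2 to 6 points per rescued patient, and no offset from weaning. The Week 8 figure of 0.08 to 0.24 points per affected patient assumes 25 patients with a score. The gap limits what the Week 26 mean can support; it does not show that the reported effect will be overstated.

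Separately, Protocol 6.6 lists rilonacept among therapies not allowed during the study, while 6.7 says that it may be added for recurrence. The two sections must be reconciled.

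**What to change.** Keep the all-data summary as planned. Add the following to Table 17 for Week 26, and to Table 16 for Week 8:

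1. The number of patients with a pericarditis or pain drug started, restarted or increased after Day 1, judged against the dose in use just before. This wording captures a drug weaned in the extension period and then resumed at its former dose.
2. The pain change shown separately for patients with and without such a change.
3. As a labelled supplementary row, the mean change with scores after that point set to baseline.

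This needs no inference or new data, and no change to patient care. It handles an observed event and is not imputation of missing data, so it does not conflict with Protocol 11.4 or SAP 9.2.

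The cost is some derivation from drug indication, dose and dates. Partial start dates need a rule: SAP 9.5.2 sets a date with a missing month to January 1, which could place an added drug before Day 1, and it gives no rule when only the day is missing. The supplementary figure will look less favourable whenever patients with added therapy improved.
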